**Table 2.1 Summary of primary and secondary endpoints**

Primary Endpoints	Indicator	Source
Maternal virologic non-suppression	HIV RNA $\geq 1000$ copies/mL	Maternal study visits at 6 wk, 6, 12, 18, 24 mo, and record abstraction for routine VL.
Retention	Seen within 2 weeks of scheduled visits	Record abstraction for scheduled clinic visits throughout study.
Loss to follow-up	Not seen in clinic for $\geq 6$ months	
Infant HIV-free survival	HIV DNA and antibody results, and mortality	Record abstraction, infant study visits, verbal autopsy.
Secondary Endpoints	Indicator	Source
Drug Adherence	Pharmacy: % days covered since last refill Self-report: % doses taken in last 30 days *pharmacy data viewed as primary analysis of secondary endpoint	Pharmacy: record abstraction throughout study Self-report: questionnaire at study visits
Maternal drug resistance	OLA	Resistance assay in mothers with virologic failure

### 3. SAMPLE SIZE CONSIDERATIONS

#### a. Analyses based on comparison of proportions

Assuming alpha=5%, power=80%, 2-sided test, 1:1:1 allocation ratio, with a sample size of 275 per arm, we would have sufficient power to detect an increase in retention or increase in virologic suppression (inverse of virologic failure) from 75% (control) to  $\geq 85\%$ , allowing for 10% attrition; we will also be able to detect an increase in ARV adherence from 85% to  $\geq 95\%$  (Table 6). Thus, the total cohort sample is 825 women. We could see a difference from 75% to 85% between control and unidirectional SMS and additionally detect a difference between uni- and bidirectional SMS (85% to 95%). Similarly, we will have sufficient power to detect an increase in infant HIV-free survival from 85% to  $\geq 95\%$ .

*Sample size for unidirectional or bidirectional SMS vs. control or unidirectional vs. bidirectional; gray shading shows cells with sufficient power and n is number per arm*

Intervention	Prevalence of outcome	Control			
		70%	75%	80%	85%
	85%	120	250	906	-
	90%	62	100	199	686
	95%	35	49	75	140

#### b. Analyses based on survival analysis

Assuming alpha=5%, power=80%, 2-sided test, 1:1:1 allocation ratio, with a sample size of 275 per arm, and 10% attrition, we will have sufficient power to

detect a Hazard Ratio (HR) of  $\leq 0.65$  in virologic failure, assuming an incidence rate of 25 per 100 person years (pys) in the control arm; a HR of  $\leq 0.55$  in drug resistance, assuming an incidence rate of 15 per 100 pys in the control arm; a HR of  $\leq 0.65$  in loss-to-follow-up, assuming an incidence rate of 25 per 100 pys in the control arm; and a HR of  $\leq 0.50$  in infant HIV or mortality (inverse of HIV-free survival), assuming an incidence rate of 10 per 100 pys in the control arm.

*Sample size for unidirectional or bidirectional SMS vs. control or unidirectional vs. bidirectional; gray shading shows cells with sufficient power and n is number per arm*

HR	Incidence in control			
	10%	15%	20%	25%
0.65	593	396	297	238
0.60	435	290	218	175
0.55	327	218	164	131
0.50	251	167	126	101

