## 2. STUDY ENDPOINTS

Primary study endpoints:

1. **Virologic non-suppression** will be defined for the primary endpoint using plasma viral load cut-off HIV RNA  $\geq 1000$  copies/mL for primary endpoint based on sample detection limits. A secondary cutoff at assay limit of detection (20c/ml for plasma and 839c/ml for DBS) will also be assessed.
2. **Retention in care** will be assessed based on medical record review of clinic attendance for scheduled clinical visits. Retention will be defined per participant as the proportion of scheduled visits to date attended within 2 weeks of their scheduled time and will be evaluated at 12 and 24 months postpartum. Loss to follow-up will be defined as no clinical visits for at least 6 months and will be evaluated at 12 and 24 months postpartum. Initial analyses will examine the 0-365 day interval and the 0-730 day interval.
3. **Infant HIV-free survival** will be assessed using infant HIV test and infant mortality data.

Secondary endpoints:

1. **ART adherence** will be assessed based on pharmacy refill data. For each refill period throughout the study, the proportion of days covered will be based on timing of refill collection. Self-reported adherence will also be assessed at study visits using a standardized questionnaire of the number of pills missed in the last 30 days and calculating percent adherence based on the expected number of doses taken. Self-reported adherence will be compared in secondary analyses.
2. **Drug resistance** will be assessed as detection of drug resistance mutations from plasma of women with HIV RNA  $\geq 1000$  copies/mL using the Oligonucleotide Ligation Assay (OLA).

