#### Primary

1. **Viral non-suppression (virus detected at  $\geq 1000$  copies/mL):** Generalized estimating equations (GEE) with log-binomial link will be used to compare the 2-way or 1-way arms versus control arm for prevalence of viral non-suppression at any time during follow-up. All available data will be used after enrollment and  $\geq 4$  months since ART start, but any observed unsuppressed VL within 30 days after an unsuppressed VL will be excluded. As secondary analyses, Andersen-Gill analysis will be used to compare incidence of viral non-suppression in the 2-way or 1-way arms versus control arm at any time during follow-up. The proportions of women ever experiencing viral non-suppression as well as the cumulative incidence by delivery, 180 days postpartum, 365 days postpartum, and 730 days postpartum will be compared between arms by log-binomial regression.
2. **Retention in care.** GEE with log-binomial link will be used to compare arms for proportion of visits attended within 2 weeks of scheduling throughout study follow-up. The proportions of women lost to follow-up by 12 and 24 months postpartum will be compared between study arms by log-binomial regression.
3. **Infant HIV-free survival.** Incidence of infant HIV acquisition or death will be compared between study arms using Cox proportional hazards regression.

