**Adherence**

\$Self-reported adherence <95% over entire

follow-up (%)

\$Refill-based adherence <95% over entire

follow-up(%)

\$ Compared by GEE Log-binomial regression

& Compared by Andersen-Gill regression

^ Compared by Cox proportional hazards regression

\* Compared by Log-binomial regression

+ Exploratory comparison

\*\* All available VL after enrollment and  $\geq 4$  months after ART start will be included

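### SAP 3b gives one survival-based power figure for loss to follow-up; it fits the planned 24-month comparison but not the planned 12-month one

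*SAP*

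**What the plan says.** The power statement is in SAP 3b, the survival-analysis part of the sample size section. Its premises are "Assuming alpha=5%, power=80%, 2-sided test, 1:1:1 allocation ratio, with a sample size of 275 per arm, and 10% attrition". Among several endpoints it claims a detectable hazard ratio of 0.65 or less "in loss-to-follow-up, assuming an incidence rate of 25 per 100 pys in the control arm". The HR 0.65 row of the accompanying table reads "593 396 297 238", so the cell for 25% incidence is 238 per arm. No time point is attached to the claim.

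The endpoint is defined in SAP section 2: "Loss to follow-up will be defined as no clinical visits for at least 6 months and will be evaluated at 12 and 24 months postpartum". The next sentence there says "Initial analyses will examine the 0-365 day interval and the 0-730 day interval". Table 2.1 lists loss to follow-up among the primary endpoints.

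The planned test is in SAP 5.3, second primary endpoint: "The proportions of women lost to follow-up by 12 and 24 months postpartum will be compared between study arms by log-binomial regression". In Table 5.2 the loss-to-follow-up row carries an asterisk, which the legend explains as "Compared by Log-binomial regression". Neither place ranks 12 months against 24 months.

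**The concern.** The power in 3b is expressed as a hazard ratio, but 5.3 contains no time-to-event analysis of loss to follow-up. Where the SAP wants such an analysis it names one: Cox regression for infant HIV-free survival and drug resistance, and Andersen-Gill for the incidence of non-suppression.

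One stated power therefore has to serve two binary comparisons with different amounts of follow-up, and it cannot be right for both. Because the SAP treats the two time points alike, nothing tells the reader that the 3b figure fits only one of them. At stake is how a null 12-month result on a primary endpoint is read. If 80% is taken to apply, that result counts as fair evidence against a hazard ratio of 0.65. On 3b's assumptions the test would miss that effect roughly 28–47% of the time.

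**Working it through.** **Inputs from SAP 3b:** two-sided 5%; 275 per arm; 10% attrition, so 275 × 0.9 = 247.5; control rate 0.25 per person-year; HR 0.65, so intervention rate 0.25 × 0.65 = 0.1625. **From SAP sections 2 and 5.3:** comparisons at 1 and 2 years postpartum. **Assumed, not in the documents:** exponential time to loss, and 0.3 years of antenatal time at risk where stated.

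**Step 1. The plan's own figure.** Freedman's formula gives ((1 + 0.65)/(1 − 0.65))² × (1.96 + 0.8416)² = 174.4, so 175 events. Two years of linear person-time yield 0.25 × 2 × 1.65 = 0.825 expected events per pair of women. Then 175/0.825 = 212.1, and 212.1/0.9 = 235.7, so 236 per arm against 238 stated. With one year the same calculation gives 175/0.4125 = 424 before attrition. The 238 is therefore a two-year figure. The formula behind the whole table was not identified: this variant misses the HR 0.50 row by about 4–5%. Step 3 does not depend on it.

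**Step 2. Cumulative risks**, 1 − exp(−rate × T):
- T = 1.0: 22.1% v 15.0%
- T = 1.3 (12 months plus 0.3 antenatal years): 27.7% v 19.0%
- T = 2.0: 39.3% v 27.7%
- Rate read as a one-year risk: 25% v 25% × 0.65 = 16.25%

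**Step 3. Power of the binary comparison**, with p̄ the mean of the two risks:

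Φ{ [ |p₁ − p₂|√n − 1.96√(2p̄(1 − p̄)) ] / √(p₁(1 − p₁) + p₂(1 − p₂)) }

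For T = 1.0 and n = 247.5: (0.0712 × 15.73 − 1.96 × 0.5498)/0.5475 = 0.078, and Φ(0.078) = 53%.

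| Comparison | 247.5 per arm | 275 per arm |
|---|---|---|
| 12 months, T = 1.0 | 53% | 57% |
| 12 months, T = 1.3 | 63% | 67% |
| 12 months, 25% v 16.25% | 67% | 72% |
| 24 months, T = 2.0 | 78% | 82% |

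Exact enumeration of the Wald test on the log risk ratio, with 248 per arm, agrees: 52.6% at T = 1.0, 67.0% for 25% v 16.25%, and 78.2% at T = 2.0.

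**Step 4. Does the model matter?** Schoenfeld's approximation for a Cox analysis over 2.0 years uses 247.5 × (0.3935 + 0.2775) = 166 events, or 184.5 events with 275 per arm. Power is Φ(½√events × |ln 0.65| − 1.96) = 79% and 83%. That is about one point above the 24-month binary test.

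**Step 5. Size needed at 12 months.** For 80% power, 22.1% v 15.0% needs 467 evaluable women per arm and 25% v 16.25% needs 335. Allowing for 10% attrition, that is 519 and 373, against 275 planned.

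**The case against.** Much of the case on the other side stands.

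- **3b is not miscalculated.** Its 238 is closely reproduced, it makes no explicit 12-month claim, and the SAP's follow-up runs to 2 years postpartum. An earlier look at the same endpoint always has less power. This is right. The defect is that the figure is not tied to a time point while 5.3 gives the two tests equal standing.
- **A reader might infer that choosing log-binomial over Cox regression loses the power.** It does not: at 24 months the two differ by about one point.
- **A reader might infer that the 12-month test is close to a coin toss.** That needs the least favourable inputs together. Deducting 10% attrition is doubtful for an endpoint that is itself loss, is read from clinic records and is analysed by intention to treat. Women also enrol in pregnancy, so some antenatal time may count. With 275 per arm and 0.3 antenatal years the figure is 67%. Every variant tried still falls below 80%.
- **A reader might infer that the 6-month-gap rule weakens the planned test in particular.** If the gap must be completed inside the window, a Cox analysis loses the same time at risk. At 1.5 years it has 69–74%, against 68–73% for log-binomial.
- **SAP 3a already powers a comparison of proportions for retention, 75% to 85%.** Read as 25% v 15% lost, this has about 80% power with 248 per arm. But 3a does not name loss to follow-up, section 2 measures retention separately as on-time visit attendance, and the implied hazard ratio is ln 0.85/ln 0.75 = 0.56. That is a larger effect than the 0.65 in 3b.

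**Conclusion.** The point holds as a mismatch between the power statement and the planned tests, with a shortfall at 12 months only. On 3b's rate and hazard ratio, the 24-month comparison has 78–82% power, about as stated. The 12-month comparison has 53–57% with 1.0 year at risk, 63–67% with 0.3 antenatal years added, and 67–72% with the rate taken as a one-year risk. The strict conversion of the rate gives the low end. These figures rest on a constant hazard and on 247.5 to 275 women per arm. The documents do not support a claim that 3b is arithmetically wrong or that log-binomial regression is an unsuitable model here.

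**What to change.** In SAP 3b, say that the loss-to-follow-up figure applies to the 24-month comparison (about 78–82%), and give the 12-month power as about 53–72%, depending on time at risk and attrition. In SAP 5.3, name 24 months as the main loss-to-follow-up test and 12 months as supportive.

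A Cox analysis of time to loss is optional. It adds about one power point and would need a rule for women who return after a gap, so it is not required to correct the statement.

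The cost is a few sentences of SAP text and a less favourable stated figure at 12 months. No new data or change of model is needed.

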### 4. USE OF INTENTION-TO-TREAT AND PER-PROTOCOL ANALYSES

Analysis of primary outcomes will be by intention to treat (all participants).

## 5. STATISTICAL ANALYSES

[figure not shown]
### 5.1 Study accrual

Per CONSORT guidelines, we will report the number of individuals who:

1. Underwent screening
2. Met inclusion criteria
3. Did not meet inclusion criteria (and reasons)
4. Enrolled in the study and were randomized
5. Treated as per study protocol

The number of individuals enrolled and randomized per study month will be presented in a figure by study arm. No formal statistical testing will be performed. See Figure 5.1.

### **Figure 5.1 – Trial profile**

## 5.2 Baseline Characteristics

We will describe the distribution of baseline characteristics, using summary statistics appropriate for the measurement scale. We will present these summary statistics in tables both pooled and by study arm (see Table 5.2). To determine if the randomization resulted in balanced groups, baseline characteristics will be compared between randomization groups using Chi-square tests for categorical variables and the Kruskal-Wallis test for continuous variables.

**Table 5.1 Baseline characteristics: shell table**

	Overall	Control	One-way	Two-way
	n (%) or median (IQR)			
Clinic:				
Ahero				
Bondo				
Mathare				
Riruta				
Siaya				
Rachuonyo				
Sociodemographic				
Age (years)				
<8 years of education				
Monthly household income (KES)				
Married / cohabiting				
Employed				
Shares phone				
Can read SMS unassisted				
Can write SMS unassisted				
Obstetric				
Primigravida				
Pregnancy intended				
Gestational age (weeks)				
HIV/ART				
Time since HIV diagnosis (years)				
On ART				
Time since ART start (years)				
HIV status disclosed to partner				
ART regimen				
AZT + 3TC + NVP				
AZT + 3TC + EFV				
TDF + 3TC + LPV/r				
TDF + 3TC + NVP				
TDF + 3TC + EFV				
TDF + FTC + EFV				
Other				
VL $\geq$ 1000 copies/mL at enrollment				
Total				

Established ART (>4mo)

New ART ( $\leq$ 4mo)

CD4 at enrollment

### 5.3 Analysis of study endpoints

Analyses will be adjusted for baseline imbalances in randomization arms.

#### Primary

1. **Viral non-suppression (virus detected at  $\geq 1000$  copies/mL):** Generalized estimating equations (GEE) with log-binomial link will be used to compare the 2-way or 1-way arms versus control arm for prevalence of viral non-suppression at any time during follow-up. All available data will be used after enrollment and  $\geq 4$  months since ART start, but any observed unsuppressed VL within 30 days after an unsuppressed VL will be excluded. As secondary analyses, Andersen-Gill analysis will be used to compare incidence of viral non-suppression in the 2-way or 1-way arms versus control arm at any time during follow-up. The proportions of women ever experiencing viral non-suppression as well as the cumulative incidence by delivery, 180 days postpartum, 365 days postpartum, and 730 days postpartum will be compared between arms by log-binomial regression.
2. **Retention in care.** GEE with log-binomial link will be used to compare arms for proportion of visits attended within 2 weeks of scheduling throughout study follow-up. The proportions of women lost to follow-up by 12 and 24 months postpartum will be compared between study arms by log-binomial regression.
3. **Infant HIV-free survival.** Incidence of infant HIV acquisition or death will be compared between study arms using Cox proportional hazards regression.

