Eligibility	
 • HIV-infected women \geq 14 years • Daily access to mobile phone and willing to receive SMS • Literacy not required if women have access to a partner/family member whom she would be comfortable to have read her the messages. • Expected continued residence in study area for the study duration • Willing to provide informed consent • Not enrolled in other studies

e) RANDOMIZATION PROCEDURES

Participants will be randomized to: 1) Simple unidirectional SMS messaging, 2) Interactive bidirectional SMS dialogue, and 3) Control, using 1:1:1 allocation. A computer-generated randomization list will be generated using random block sizes in STATA. The allocation codes will then be put in sequentially numbered sealed envelopes. Participants and study will be un-blinded to randomization arms.

f) DATA COLLECTION PROCEDURES

Women will be followed during pregnancy and for two years postpartum; all clinical care will be managed through the existing MCH and CCC infrastructure. Because the study aims to determine mHealth benefits in a routine clinic setting, specific ANC/PMTCT/HIV services will be delivered by the MOH programs with minimal clinic interactions with study personnel. The study team will abstract data regarding clinic attendance, pill refills, infant health and infant HIV status from the PMTCT program registry, labor and delivery ward, pharmacy and peer counselors registers. Viral load and infant HIV testing results will be abstracted from the national electronic viral load dashboard. We will make check-in calls to all participants regardless of study arm at 1 month and 1 year post-EDD. This will be done to ascertain mother's delivery status, infant status, and that phone number is up to date. Check-in calls will be done by data management teams and will call the participants contacts if they fail to reach study participant.

The study visit schedule will be: enrollment (any time in pregnancy), 6 weeks postpartum, then every 6 months up to 24 months. At each visit a standardized questionnaire will be administered using a tablet-based system (Open Data Kit, ODK) developed by the UW Department of

[figure not shown]

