Computer Science and Engineering collaborators. Between study visits, data will be obtained from patient records in order to inform personalized, dynamic messaging. For example, if a participant in one of the intervention arms misses an appointment an appropriate SMS will be sent to address this absence and encourage the participant to reschedule. If a participant in the bidirectional arm does not respond after receiving two weekly messages, she will receive a check-in message asking if she is receiving messages. The study nurse will review clinical records daily to check for missed appointments, deliveries, clinic visits, infant immunizations, or any clinic contact from study participants. Delivery information from women will be obtained at 6 weeks postpartum and data abstracted from records at MCH-linked maternity centers. Follow-up will continue until 24 months postpartum.

In order to ensure completeness of clinic record abstraction for the study period, photographs will be taken at study exit of participants' CCC cards. All identifiable information, including name, date of birth, CCC number, ANC number and address will be covered with paper, and the record will be labeled with the participant's study ID only. Photographs will be transferred to a password-protected computer and secure server within 1 day of the photograph being taken and permanently deleted from the device used to capture the image. At the final study visit, in order to verify the data collected during abstraction, we will measure the height, weight, and mid-upper arm circumference of participants and their infants.

We will collect 14 ml maternal plasma samples for CD4 count, HIV viral load, and suspected drug resistance testing for mothers and 0.5 ml for HIV DNA DBS and HIV antibody testing for infants at all study visits. SOPs will be used to guide venipuncture procedure. The study will obtain viral loads for all participants. However, if the Kenyan MOH incorporates routine HIV viral load testing on a national scale and the testing intervals are similar to those proposed by the study, we will utilize viral load results from the standard of care rather than repeat viral loads.

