**Table 5.2 Study endpoints: shell table**

	Overall	Control	One-way	Two-way	p-value (one-way vs. control)	p-value (two-way vs. control)	p-value (either intervention vs. control)	p-value (one- way vs two- way)+
MATERNAL OPTION B+								
Virologic non-suppression ever (VL $\geq$ 1000 copies/mL) (n, %)								
Prevalence of virologic non-suppression **								
Incidence of virologic non-suppression (per 100 py)								
*With virologic non-suppression by delivery (%)								
*With virologic non-suppression by 180 days postpartum (%)								
*With virologic non-suppression by 365 days postpartum (%)								
*With virologic non-suppression by 850 days postpartum (%)								
Retention								
Scheduled clinic visits attended on time since enrollment per participant (%)								
To 12 months postpartum								
To 24 months postpartum								
*Loss to follow-up (%)								
By 12 months postpartum								
By 24 months postpartum								
^Infant HIV and mortality								
Infant HIV incidence (per 100 py)								
Infant mortality (per 1000 live births)								
Infant HIV-free survival (per 100 py)								

Drug resistance (DR) ^Cumulative incidence of DR per 100 py *DR at 6 months postpartum (%) *DR at 12 months postpartum (%) *DR at 24 months postpartum (%)**							
---	--	--	--	--	--	--	--

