Modification of VL analysis approach	26 May 2020	5.0	We will stratify the study population by VL at enrollment, and conduct 2 separate survival analyses: 1. Incidence of virologic suppression among participants with unsuppressed VL at enrollment. 2. Incidence of virologic failure among participants with suppressed VL at enrollment.	Risk of virologic non-suppression will be analyzed as a repeated measure by GEE with Poisson link.  Previously specified analyses of incidence of virologic suppression and virologic failure will be performed as exploratory analyses.	The stratified analysis did not use all available data, or allow us to probe changes in the intervention's effect over time. In order to maximize power and allow estimation of effect modification by peripartum timepoint, we will treat virologic non-suppression as a repeated measure.
Removal of secondary analysis with imputation of missing VL data	26 May 2020	5.0	A secondary analysis will be performed using multiple imputation by MCMC to impute VL 6 months after the time of last measurement.	No imputation will be performed.	Our dataset has 10% missing data at 24 months postpartum but >40% missing data at 18 months postpartum. Imputation of the one final VL measure would not address the problem of missing VL for a repeated measures analysis, since the bulk of missingness is at intervening timepoints. Imputation of intermediate VL given such high levels of missingness is not advisable.

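### The 30-day exclusion in the primary viral-load GEE depends on the result itself; the effect on the arm ratio is unknown and probably small

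*SAP*

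**What the plan says.** Section 5.3 of the SAP compares each SMS arm with control by a repeated-measures GEE for the prevalence of non-suppression. It uses every VL taken after enrollment and at least 4 months after ART start, except that "any observed unsuppressed VL within 30 days after an unsuppressed VL will be excluded". An Andersen-Gill analysis of incidence and per-woman comparisons (ever non-suppressed, and cumulative incidence at four time points) follow as secondary analyses.

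Table 5.2 has a row "Prevalence of virologic non-suppression" whose footnote begins "All available VL after enrollment and" and says that these values will be included. It mentions no 30-day exclusion.

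VLs come from two streams. Table 2.1 lists study visits at 6 weeks and 6, 12, 18 and 24 months, "and record abstraction for routine VL". The protocol (Phase 2, Data collection procedures) says: "Viral load and infant HIV testing results will be abstracted from the national electronic viral load dashboard". It adds that if national routine testing is introduced at similar intervals, "we will utilize viral load results from the standard of care rather than repeat viral loads".

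Table 6.1 does not record the 30-day rule or a reason for it. Section 5.3 does not say whether the enrollment VL, or a VL that has itself been excluded, can serve as the earlier member of a pair.

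**The concern.** Take two VLs from one woman less than 30 days apart. If both are unsuppressed, the second is dropped. If the second is suppressed, it stays. If the first is suppressed, the second stays whatever its value. Selection is therefore on the outcome. Concordant unsuppressed repeats leave both numerator and denominator, while concordant suppressed repeats add to the denominator only.

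The rule makes sense for an event count such as the Andersen-Gill analysis, where it stops one viremic episode counting twice. In a prevalence it biases the estimate downward. The contrast between arms is distorted if close repeats are more common in one arm, or if viremia persists differently across such repeats. An analyst following the Table 5.2 footnote would also build a different primary dataset from one following section 5.3.

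**Working it through.** **Figures in the plan.** None concerns the 30-day rule. The plan's assumption for this endpoint is "increase in virologic suppression (inverse of virologic failure) from 75% (control") to at least 85%, so 25% and 15% non-suppressed. Its 250 per arm reproduces (two-sided 5%, 80% power, pooled variance: 249.98), which fixes the inputs but has no bearing on the rule.

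**Assumed inputs.** p is true non-suppression (25% or 15%, the same in both arms, so the true ratio is 1). d is the number of 30-day repeats per index VL. a is the chance that a repeat after an unsuppressed VL is also unsuppressed. To keep prevalence at p, the chance of an unsuppressed repeat after a suppressed VL is b = p(1−a)/(1−p). All values of d and a are assumptions.

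**1. Repeats taken regardless of result.** Under the written rule, with independence weights,

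prevalence = [p + d(1−p)b] / [1 + d{(1−p) + p(1−a)}].

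Example with a = 1 and p = 0.25: at d = 0.05, 0.25/1.0375 = 0.2410; at d = 0.10, 0.25/1.075 = 0.2326; ratio 0.965.

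Null ratio with the lower rate in control and the higher in the SMS arm (each cell spans p = 25% and 15%):

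| Repeats, control v SMS | a = 1 (worst case) | a = 0.7 |
|---|---|---|
| equal | 1.00 | 1.00 |
| 1% v 2% | 0.992–0.993 | 0.994–0.995 |
| 2% v 5% | 0.976–0.978 | 0.983–0.985 |
| 5% v 10% | 0.961–0.965 | 0.973–0.976 |
| 5% v 15% | 0.925–0.933 | 0.948–0.954 |

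Swapping the arms inverts the ratio: 5% v 10% at a = 1 becomes 1.036–1.041. The documents give no basis for either direction.

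**2. Exchangeable working correlation.** The SAP names no correlation structure, so two-arm GEEs were simulated: 275 women per arm, 4 index VLs each, within-woman correlation 0.4, robust standard errors, 3000 runs. The ratios are closer to 1. With full agreement they are 0.996, 0.987–0.988, 0.979–0.982 and 0.958–0.963 for the four unequal rows. With persistence of 75–78% they are 0.997, 0.991, 0.985–0.986 and 0.971–0.973. Persistence differs from the 70% in the table, so the two sets with imperfect agreement are not like for like.

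**3. False-positive rate, nominal 5%.** For gaps of up to 5 points it is 4.6–6.3%, against 4.3–6.0% for a result-blind rule in the same runs. At 5% v 15% it is 6.0–9.8% (independence) or 5.1–6.3% (exchangeable).

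**4. Repeats only after an unsuppressed VL**, with a share s = 0.3 re-suppressing. The written rule gives p/(1 + pds). At 5% v 10% the null ratio is 0.996–0.998 (exchangeable 0.993–0.994); at 5% v 30% it is 0.982–0.989 (exchangeable 0.967–0.970). Keeping every VL gives [p + pd(1−s)]/(1 + pd). At 5% v 30% that is 1.10–1.13 (exchangeable 1.03–1.04), further from 1 than the written rule.

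**5. A true effect.** With a true ratio of 0.60 and equal repeat rates, the written rule gives 0.590–0.598 and the result-blind rule 0.596–0.600.

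**The case against.** The strongest reply is that no harm is shown. Equal repeat rates leave the null ratio at 1.00, and nothing in the documents suggests that the arms would differ. Close pairs are probably few: after 6 weeks the study VLs are about 6 months apart, routine results may replace study VLs, and Table 6.1 reports more than 40% missing at 18 months. In the simulated setting the effective number of VLs per arm is 1100/(1 + 3 × 0.4) = 500, so the standard error of the log ratio is about 0.11 (p = 25%) to 0.15 (p = 15%). The worst-case bias is then about 0.06 standard errors at 1% v 2% and about 0.3 at 5% v 10%. All of this stands. The larger figures need a 10-point gap between arms, and 4 VLs per woman with correlation 0.4 are single assumed values.

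The rule also does something useful in the GEE: if repeats are confirmatory, it removes most of the distortion that keeping every VL would cause. That stands too, and it argues against simply deleting the rule, not against making it result-blind.

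The May 2020 entries in Table 6.1 already describe the collected data, so changing a primary rule now would be data-aware. That calls for a dated log entry and for both results to be reported. The per-woman analyses are not diluted by suppressed duplicates, but they estimate something else and are only a partial cross-check.

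None of this answers the two textual points: inclusion depends on the outcome, and the footnote contradicts section 5.3.

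**Conclusion.** The concern holds, as a minor point. It is certain from the text that the written rule selects on the outcome and lowers estimated prevalence, and that the Table 5.2 footnote disagrees with section 5.3.

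The size is unknown and may be negligible. Equal repeat rates do no harm under the null and move a true ratio of 0.60 by at most about 0.01. Rates of 5% v 10% in repeats taken regardless of result shift the null ratio by about 1.5% to 4%, depending on persistence and working correlation. A shift of around 7% needs 5% v 15%, full agreement and independence weights. The direction follows whichever arm has more repeats. Confidence is high in the defect and low that it matters in size.

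**What to change.** In section 5.3, for the prevalence GEE, keep the first VL and drop any later VL within 30 days of a retained VL, whatever its result. State whether the enrollment VL can open a window. Keep the written rule for the Andersen-Gill count and report it in the GEE as a sensitivity analysis. Do not delete the exclusion outright, given step 4 of the working. Align the Table 5.2 footnote and log the change in Table 6.1. Report VLs and 30-day repeats by arm; those counts will show whether the issue is material.

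The cost is one sentence, one footnote and a re-run. The result-blind rule also drops discordant repeats. At 70% persistence the discordant share of dropped repeats is 2p(0.3), or 15% at p = 25% and 9% at p = 15%. Half of these (4.5–7.5%) are a new VL at or above 1000 after a suppressed one; they stay in the per-woman and incidence analyses. In simulation, power for a true ratio of 0.60 differs by at most 0.3 points at 5% repeats in both arms. At 20% repeats it is at most 1.5 points lower (82.3% v 83.8%).

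One limit remains. Retests prompted by a high result but taken after day 30 are untouched by either rule. At 5% v 30% they give a null ratio of 1.10–1.13 (independence) or 1.03–1.04 (exchangeable) under both, so the timing of retests should be reported by arm as well.
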